11.5 Protocol/ GCP non-compliance

The CI should report any non-compliance to the trial protocol or the conditions and principles of GCP to the sponsor as soon as they become aware of it.

11.6 End of trial

The end of the trial is defined as the date of final data capture to meet the trial endpoints.

11.7 Archiving

The Trial Master File (TMF) will be held in a secure locked personal office of the CI which itself is located in a secure staff only access department area at LUHFT. Essential documents pertaining to the trial shall not be destroyed without permission from the Sponsor. Electronic copies of the study documents will also be archived on the password-protected encrypted NHS server at LUHFT for a minimum of 10 years.

12 Statistical considerations

12.1 Randomisation

After confirmation of eligibility, randomisation will take place by contacting LCTC. Participants will be randomised using minimisation to ensure balanced treatment allocation by several clinically important stratification factors including lesion site and surgical technique. A randomisation allocation ratio of 1:1 will be used.

12.2 Outcome measures

12.2.1 Primary outcome measures

The primary outcome of this study will be pain following procedure. This will be measured using the visual analogue scale (VAS) which is a validated pain rating scale first used by Hayes and Patterson in 1921 [9]. Self-reported pain severity is recorded by marking a point on a 10cm line that represents a continuum between 'no pain' at one end and 'worst pain' at the other. VAS pain scores preoperatively and on days 1, 2, 4, 7, 14 and 30 postoperatively will be recorded.

12.2.2 Secondary outcome measures

This will include data on:

- Post-operative analgesia usage (including drug used, dose, route and frequency)
- Post-operative complications by Clavien Dindo Classification including wound infection and bleeding rates
- Length of stay in hospital
- Readmission to hospital within 30 days post operatively
- Bleeding events including primary (24 hours post operatively) and secondary (day 1 to 30 post operatively) haemorrhage
- Return to operating room within 24 hours post operatively
- Return to operating room within 30 days post operatively
- Surgeon survey regarding ease of PuraBond® use
- Time taken to normal oral dietary intake (days)
- Any health economic benefits of PuraBond® use.

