3.2 Study objectives

The aim of this study is to assess whether intraoperative use of the haemostatic agent PuraBond® is associated with decreased levels of pain postoperatively following wide local excision procedures for oral or oropharyngeal mucosal lesions. We hypothesise that patients treated with such agents will have better post-operative pain scores compared to those treated without.

4 Study design

PuraBond® PROOF is a prospective, single centre, parallel group randomised controlled trial (RCT). Patients eligible for the study must have clinically suspected or histologically confirmed dysplasia or malignancy in the oral cavity or oropharyngeal subsites. Their primary lesion must be considered resectable via a transoral approach. After informed consent, patients will undergo baseline assessment of pain levels prior to surgery and demographic data will be collected. Surgery may or may not involve laser use to the primary site.

Suitable patients will be stratified prior to randomisation by lesion site (oral cavity or oropharynx) and whether or not the surgical technique will involve laser resection. Depending on which arm the participant is allocated to, PuraBond® may or may not be applied to the surgical bed intraoperatively. It is important to note that both treatments are routinely used in these operations and PuraBond® use will fall completely within its license in this study.

Using surgical site and technique to clinically stratify patients is important as standard post operative analgesia management differs between these groups (see table below). It is important that data collected from this trial represents real world evidence and thus, pre and post operative analgesia agents used will be recorded by analysing patient's prescriptions rather than. restricting analgesia prescriptions and changing current standard of care. This means this trial will not lack generalisability and will not limit the relevance of its results to real world practice.

Medication	Oropharyngeal surgery		Oral cavity surgery
	TOLR	No laser used	
Paracetamol	✓	✓	✓
Ibuprofen	✓	✓	✓
Codeine	✓	✓	✓
Morphine	✓	Not routinely used	Not routinely used
Oxycodone	X	Not routinely used	Not routinely used
Chlorhexidine	X	X	✓
Gelclair®*	✓	X	✓
Benzydamine 0.15% solution	✓	✓	✓
Pregabalin	✓	X	X

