*Please note: Patients enrolled in PuraBond® PROOF will not be prescribed Gelclair® post operatively. Gelclair® is a viscous gel used orally that may confound any results of PuraBond use. It is a product licensed for treatment of oral mucositis in in oncology, hence use in our patient cohort is considered off label.

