The operating surgeon will be informed by LCTC regarding the patient's treatment arm allocation. Due to the packaging of PuraBond® within pre-filled and labelled syringes, attempts to completely blind clinicians intraoperatively are not feasible. However, the patient, the assessors of postoperative outcomes and the study co-investigators will be blinded.

8 Trial endpoint assessments

The aim of the PuraBond® PROOF trial is to determine whether PuraBond® application intraoperatively on the surgical field significantly reduces postoperative pain in head and neck transoral operations. Assessment of secondary clinical outcomes such as hospital stay and time till oral intake alongside post operative complications are also important points to record consequently. The study will also briefly consider any health economic benefits of PuraBond® use.

Details of the assessments required are included in the CRF and are outlined below in the schedule of trial assessments (see section 8.4). With regards to the timing of assessments, the date of transoral surgery and thus whether PuraBond® is applied or not is classified as day 0.

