8.3 Post-operative assessments

8.3.1 Post-operative discharge

On discharge day, the following data will be recorded:

- Length of stay in hospital (days)
- Intraoperative complications
- Time till commencement of oral intake

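### Analgesia usage is a secondary outcome, but prescription review is its only stated source and section 8 gives it no collection point, so use after discharge may be poorly measured

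*Combined protocol and SAP*

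**What the plan says.** Section 12.2.2 puts first among its ten secondary outcomes "Post-operative analgesia usage (including drug used, dose, route and frequency"). It attaches no time window.

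The source is given in section 4, which says that "pre and post operative analgesia agents used will be recorded by analysing" the patient's prescriptions, as an alternative to "restricting analgesia prescriptions and changing current standard of care". The one exception is in the footnote to the analgesia table: "Patients enrolled in PuraBond® PROOF will not be prescribed Gelclair® post operatively".

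Section 8 then sets out what is collected and when. It says: "Details of the assessments required are included in the CRF and are outlined below in the schedule of trial assessments (see section 8.4"). The lists are in 8.1 (baseline), 8.2 (day 0), 8.3.1, which opens "On discharge day, the following data will be recorded", and 8.3.2 (follow-up). Under 8.3.2 the calls on days 1, 2, 4, 7, 14 and 30 are optional reminders about the VAS. The scheduled day 30 call covers reoperation, complications and readmission. The patient posts back the VAS form. Pain VAS, the primary outcome (12.2.1), is scored on those six post-operative days.

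**The concern.** The outcome is defined as usage, down to dose and frequency. A prescription records an order. On the ward the two can be close, because doses are given by staff and charted. At home the patient decides how much of a supply to take and when, and the prescription does not show it. Anything obtained without a prescription would also be missed. That people in this trial do so is an assumption, since no section says it, but paracetamol and ibuprofen are standard in all three columns of the section 4 table.

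The stake is interpretation of the primary result. Analgesia is left free, so patients in more pain can take more of it, which pulls VAS scores together. If the two arms score alike, there may be no effect, or the arm with more pain may have taken more analgesia. Intake recorded near the VAS days is the evidence that helps tell these apart. If it is not collected at the time, neither a later analysis plan nor a later search of prescriptions can recover it.

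**Working it through.** The plan states no figure on this point, so the check is a reading of the sections against one another, plus two counts.

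**1. Does section 8 give analgesia a collection point?**

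| Place | Items | Naming analgesia or medication |
|---|---|---|
| 8.1 Baseline | 8 | 0 |
| 8.2 Day 0 | 4 | 0 |
| 8.3.1 Discharge | 3 | 0 |
| 8.3.2 Day 30 call | 3 | 0 |
| Total of lists | 8 + 4 + 3 + 3 = 18 | 0 |
| 8.4 Schedule rows | 18 | 0 |

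**2. Is that usual for a secondary outcome in this plan?** Tracing the 10 outcomes of 12.2.2 to rows of 8.4:

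- With their own row, 7: complications, length of stay, readmission, return to theatre at 24 hours, return to theatre at 30 days, surgeon survey, oral intake.
- Through the complications row, 1: bleeding.
- With no row, 10 − 7 − 1 = 2: analgesia usage and health economics.

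So 8 of 10 can be traced. Length of stay and readmission could also be read from hospital records, and both have a row. Being obtainable from records therefore does not explain why analgesia has none.

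**3. What does the stated source cover?** Set against the four parts of the definition:

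| Part of the outcome | In hospital | After discharge |
|---|---|---|
| Drug | Likely covered | Prescribed drugs only, if the review extends that far |
| Route | Likely covered | As above |
| Dose taken | Covered if inpatient administration records are included (not stated) | Not shown by a prescription |
| Frequency taken | As above | Not shown by a prescription |

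The gap is in the lower right: dose and frequency at home.

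**4. How many VAS days fall at home?** The expected length of stay is not given, so discharge day d is an assumption. Count the days in {1, 2, 4, 7, 14, 30} that are later than d:

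| Assumed discharge day | VAS days after discharge | Count of 6 |
|---|---|---|
| 0 | 1, 2, 4, 7, 14, 30 | 6 |
| 1 | 2, 4, 7, 14, 30 | 5 |
| 2 | 4, 7, 14, 30 | 4 |
| 4 | 7, 14, 30 | 3 |
| 7 | 14, 30 | 2 |

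Days 14 and 30 are at home in every row. Day 30 is the time point named in the synopsis objective.

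These counts show where intake is not planned to be recorded. They do not show how far actual intake would differ from what was prescribed, which the documents give no means to estimate.

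**The case against.** The best defence is that section 8 only outlines the assessments and refers to the CRF for detail, and 12.4 says all data are collected on the CRF. The CRF is not among the documents and may hold an analgesia item. The 8.4 schedule is also not a full map of the outcomes, since health economics has no row either. This stands as a limit on the claim: it concerns sections 4, 8 and 12.2.2, and the conclusion is that home use may be poorly measured, not that it will be. It does not remove the point, because the protocol presents 8.4 as the outline of what the CRF collects, and that outline contains no analgesia.

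Three stronger readings are tempting, and the documents do not support them.

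- A reader might infer that analgesia is not collected at all. Section 4 names a method, and review of records needs no patient visit.
- A reader might infer that usage is badly measured throughout. Hospital use may be captured adequately. The protocol does not say whether the prescriptions reviewed include administration records, but nothing rules it out.
- A reader might infer that the primary comparison is biased. It is not biased by this gap. Leaving analgesia free is a reasoned real-world choice, allocation is randomised with minimisation on site, neck procedure and laser use, and section 7 says: "However, the patient, the assessors of postoperative outcomes and the study co-investigators will be blinded". The comparison of pain under usual analgesia, analysed by intention to treat, remains valid. What suffers is the explanation of a null or small difference.

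A further objection is that recording intake is not free. After laser resection of the oropharynx, the section 4 table ticks seven products, and six remain once Gelclair is withheld. Asking for name, dose and times for each would put a multi-drug entry on the form that carries the primary outcome, in a trial analysed on complete cases. That stands, and it is the reason to keep any new item short.

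**Conclusion.** The point holds as a measurement gap in one secondary outcome, limited to use after discharge. Prescription review is the only stated source, it has no stated window, and none of the 18 listed items and none of the 18 schedule rows mentions analgesia. For discharge between day 0 and day 7 (assumed), 6 down to 2 of the 6 post-operative VAS days would have pain recorded at home with no matching record of intake.

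This rests on two conditions: that the CRF has no intake item, and that what patients take at home differs enough from what was prescribed to matter. Use of medicines obtained without a prescription would widen the gap, but is itself an assumption. The change should be made, because the data cannot be recovered later and the remedy is small. The primary analysis and the sample size are untouched.

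**What to change.** 1. Add an analgesia row to 8.4, marked at discharge and on days 1, 2, 4, 7, 14 and 30.
2. In section 4, state that prescription review runs from surgery to day 30, and whether it includes inpatient administration records. Keep it as the source for drug, route and prescribed dose.
3. If the CRF has no such item, add a brief one to the patient's VAS form, placed after the VAS line so that the pain score is marked first: analgesics taken in the last 24 hours, as a pre-printed tick list of the standard drugs with the number of doses of each.
4. Report analgesic use by arm descriptively. Keep the ANCOVA as the primary analysis, without adjustment for analgesia, which is itself affected by treatment.

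If the CRF already has the item, only the schedule row, the stated window and the descriptive table are needed.

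The cost is one row, one or two sentences, a short tick list on a form that patients already complete and post back, and one table. The downside is a slight burden on the form that carries the primary outcome, and some missing or inaccurate self-reports. The item would be completed by patients whom the protocol describes as blinded.

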8.3.2 Post-operative follow up

A patient phone call may be conducted on days 1,2,4,7,14 and 30 to remind them to fill in their VAS pain scores. A scheduled patient phone call on day 30 will collect the following data:

- Reoperation within 30 days
- Post operative complications

- Readmission to hospital within 30 days

They will be asked to return their VAS pain CRF to the study team via a pre-paid envelope provided.

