8.4 Schedule of trial assessments

Assessment/ Procedure	Screening and baseline	Surgery (Day 0)	Day of discharge	Follow up					
				POD 1	POD 2	POD 4	POD 7	POD 14	POD 30
Eligibility (inclusion/ exclusion criteria)	x								
Written informed consent	x								
Registration	x								
Assignment of a unique participant identification number	x								
WHO performance score	x	x							
Randomisation		x							
Pain VAS score		x	x	x	x	x	x	x	x
Participant demographics – age, gender etc.	x								
Diagnosis and proposed surgery	x	x							
TOLR/ transoral surgical excision		x							
Surgeon's survey		x							
Return to theatre within 24 hours				x					
Length of hospital stay			x						
Readmission to hospital within 30 days									x
Return to theatre within 30 days									x
Intra operative complications			x						
Post operative complications				x	x	x	x	x	x
Time till oral intake			x	x					x

9 Adverse effects and safety reporting

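### Time to normal diet is a named secondary outcome, but the collection sections describe the start of oral intake or an unspecified event, and the day-30 entry has no stated route

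*Combined protocol and SAP*

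**What the plan says.** Section 12.2.2 names the secondary outcome as "Time taken to normal oral dietary intake (days". Normal diet is not defined there or elsewhere.

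The other places that mention the item are:

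- **Section 8, introduction:** "Assessment of secondary clinical outcomes such as hospital stay and time till oral intake". It adds "Details of the assessments required are included in the CRF" and points to the schedule in 8.4.
- **Section 8.3.1:** "On discharge day, the following data will be recorded", with the item "Time till commencement of oral intake".
- **Section 8.4:** a row labelled "Time till oral intake", marked at day of discharge, POD 1 and POD 30.
- **Section 8.3.2:** "A scheduled patient phone call on day 30 will collect the following data", followed by three items: reoperation, post-operative complications and readmission. On the patient-held form it says "They will be asked to return their VAS pain CRF to the study team via a pre-paid envelope provided". The other calls are optional and serve only as reminders to complete the VAS.

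Section 12.4 plans complete-case analysis, summarises continuous data by median and inter-quartile range, and leaves further detail to a later analysis plan. Section 13.1 puts the last data collection point at one month after surgery.

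**The concern.** Starting to take anything by mouth and returning to a normal diet are two different events. A patient may take fluids or soft food soon after surgery and be back on a normal diet only later, at home. Section 9.2.1 lists pain and difficulty swallowing among the expected complications of transoral surgery, so an interval between the two events is plausible in this population.

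Staff who follow 8.3.1 would write down the earlier event. Staff who follow the 8.3.2 list would not ask about diet on day 30. The value analysed could then be start of intake under the heading of normal diet. The uncontrolled case series in section 3.1 reports oral diet resumed on day one in all thirteen patients. If trial patients start intake similarly early, that variable would vary little and could hardly separate the arms, whereas time to normal diet still might. Because one month is the last collection point, a date not asked for by then has no later planned opportunity.

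**Working it through.** The protocol gives no figure to reproduce for this outcome. The check is a comparison of passages, followed by a small count for the proposed handling.

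**1. Which event each place describes**

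| Place | Event | When recorded |
|---|---|---|
| 12.2.2 | Return to normal diet, in days | Not stated |
| 8, introduction | Oral intake, unspecified | Not stated (a statement of aims) |
| 8.3.1 | Start of oral intake | Discharge day |
| 8.4 | Oral intake, unspecified | Discharge, POD 1, POD 30 |

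The two places that instruct collection are 8.3.1 and 8.4. Neither refers to normal diet. By definition, start of intake is no later than return to normal diet, so the 8.3.1 value is at most a lower bound for the named outcome.

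**2. Routes for the POD 30 entries**

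| Row marked at POD 30 in 8.4 | Route in 8.3.2 |
|---|---|
| Pain VAS | Form returned by post |
| Readmission within 30 days | Day-30 call |
| Return to theatre within 30 days | Day-30 call (as reoperation) |
| Post-operative complications | Day-30 call |
| Oral intake | None |

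Four of the five rows have a route, and oral intake is the fifth. The POD 30 mark may well be intended for normal diet, but neither its label nor the call list says so.

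**3. Patients not yet on normal diet by day 30**

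Take an arm of 32 (section 12.3) and place patients recorded as not yet above every observed time.

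- The median uses the 16th and 17th ordered values. It is an observed number of days with up to 32 − 17 = 15 patients not yet.
- The upper quartile uses the 24th and 25th ordered values. It is an observed number of days with up to 32 − 25 = 7 patients not yet. Beyond about 7, it is reported as >30.

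So the summary planned in 12.4 can still be reported with these patients kept in. Its upper quartile reaches the limit well before its median does.

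**4. What cannot be computed**

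The documents give no times by arm for either event and no expected length of stay. The size of the difference between the two variables, and the number of patients who would reach normal diet after discharge, are therefore unknown.

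**The case against.** The best reply is that most of the machinery exists. The schedule already has a post-discharge mark for oral intake, a day-30 call is already scheduled, and the protocol places assessment detail in the CRF, which is not among the documents. The CRF may ask for exactly the right date. Post-operative complications are also on the call list, so a swallowing problem could come up there. Much of this stands: what is missing from the text is consistent wording and one line in a list. It does not remove the point. The schedule to which section 8 refers carries the unspecified label, and a reported complication supplies no date.

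Three stronger readings are tempting and are not supported:

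- **That the outcome will not be collected.** With the CRF unseen, only the protocol text can be faulted.
- **That the days between schedule marks are lost data.** The outcome is a date that can be recalled and recorded once at day 30, so the spacing of the marks does not measure loss.
- **That the complete-case rule will drop the slowest patients.** Section 12.4 does not say that an event not reached by day 30 counts as missing, and it defers detail to a later plan. It is a risk to close off, not a stated rule.

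**Conclusion.** The point holds as an inconsistency between the named outcome and its collection instructions. Section 12.2.2 promises time to normal diet, 8.3.1 collects start of intake, 8.4 does not say which is meant, and 8.3.2 gives no route for the POD 30 entry. For patients who reach normal diet after discharge, the protocol text does not clearly collect the outcome it names.

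The reach is one of ten secondary outcomes. The primary analysis and the sample size are unaffected. The conclusion rests on the protocol text alone and assumes that at least some patients resume normal diet after leaving hospital. If the CRF already asks for the date of normal diet, only the wording needs to be aligned. The correction should be made because it is cheap and because no collection point is planned after one month.

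**What to change.** 1. Use one term for the outcome in the introduction to section 8 and in 8.3.1, 8.4 and 12.2.2. Keep start of oral intake as a separate, separately labelled item.
2. Define normal diet in words a patient can answer.
3. Add to the day-30 call list in 8.3.2: *date normal diet resumed, or not yet by day 30*. Relabel the POD 30 mark in 8.4 to match, and check that the CRF uses the same wording.
4. State in 12.4 or the later analysis plan that not yet by day 30 is an observed value beyond 30 days, either censored at day 30 or ranked highest, and is not missing under the complete-case rule. Name a between-group comparison that fits that choice (time-to-event or rank-based), and report the upper quartile as >30 where it falls beyond day 30.

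The cost is one extra question at an existing call and no extra visit. The date is self-reported and recalled over up to a month, so it will be less exact than an inpatient record. The change is a protocol amendment, and possibly a CRF amendment, which section 13.2 requires the sponsor to classify. It helps only those patients whose day-30 contact is still to come when it takes effect.
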